APPENDIX 1: PREDICTED BODY WEIGHT (PBW) CALCULATION

• **Male:** PBW (in kg) = $50 + 0.91 [\text{height (cm)} - 152.4]$

• **Female:** PBW (in kg) = $45.5 + 0.91 [\text{height (cm)} - 152.4]$

Ref: Ventilation with lower tidal volumes as compared with traditional tidal volumes for acute lung injury and the acute respiratory distress syndrome. The Acute Respiratory Distress Syndrome Network. The New England Journal of Medicine 2000;342:1301-8.

Use true height if this has been measured accurately in the last few days. If not, use estimated height from measurement of the demi-arm span.

The demi-arm span should be measured using the right arm (preferably) and by measuring between the base of the fingers where the middle and ring fingers meet to the sternal notch. The patients' right arm should be extended until it is horizontal with the shoulder. Ensure the wrist is straight. The patients' arm may need to be supported.

The estimated height can then be calculated from the measured demi-arm span as follows:

• **Male:** Height (in cm) = $(1.40 \times \text{demi-arm span (cm)}) + 57.8$

• **Female:** Height (in cm) = $(1.35 \times \text{demi-arm span (cm)}) + 60.1$

APPENDIX 2: BRONCHOALVEOLAR LAVAGE (BAL) FLUID COLLECTION

Non-bronchoscopic method:

1. Pre-oxygenate the patient by increasing the FiO_2 to 1.0 for 2 minutes. The PEEP should be left on the current setting.
2. Draw up 60 ml of 0.9% saline in appropriate syringes (usually three 20 ml syringes). Prepare a clean environment as per the usual site practice for similar interventions.
3. Connect one of the 0.9% saline syringes to the upper port on the 3 way tap and point the off arrow to the other port. Ensure the blue locking device is open.
4. Introduce the BAL catheter by forwarding the catheter through connector B so that the catheter tip protrudes through the connector before connecting to the endotracheal tube.
5. Disconnect the in-line suction and ventilator and attach connector B to the endotracheal tube – the catheter should be 2 cm into the endotracheal tube. Reconnect the ventilator tubing to connector B.
6. Advance the catheter until the numbers on the catheter match the numbers on the endotracheal tube. At this point the catheter is located exactly at the distal point of the endotracheal tube.
7. Ensure the white oxygen port on the catheter is orientated to the right. This means that the internal catheter will be angled towards the right main bronchus.
8. Forward the entire catheter another 5 cm and check that the white oxygen port remains orientated to the right side.
9. Flush the catheter with 5 ml 0.9% saline. Lock the blue locking device.
10. Gently advance the inner catheter until a spongy resistance is noted (ie. the catheter is appropriately wedged in a distal bronchus).
11. Inject the first syringe of 0.9% saline, followed by 5 ml air. With the same syringe, gently hand aspirate the BAL, then do the same with subsequent syringes via the 3 way port until a minimum volume of 10ml. is obtained.
12. Withdraw the inner suction catheter until the solid black mark is outside the connector to the endotracheal tube. Unlock the blue locking device. Withdraw the entire catheter. Reconnect the in-line suction catheter and the original connectors.
13. Combine the collected BAL fluid from each syringe into a sterile container and label this as a BAL for the PHARLAP study.
14. If the patient has been assigned to the PHARLAP group, this procedure should now be followed as soon as possible by a combined open lung procedure (see page 26) if it is day 1 or a BRM if it is day 3.

Bronchoscopic method:

1. Pre-oxygenate the patient by increasing the FiO_2 to 1.0 for 2 minutes. The PEEP should be left on the current setting.
2. Draw up 60 ml of 0.9% saline in appropriate syringes (usually three 20 ml syringes). Prepare a clean environment as per the usual site practice for similar interventions.
3. Wedge the bronchoscope in the appropriate bronchus.
4. Inject the first syringe of 0.9% saline, followed by 5 ml air. With the same syringe, gently hand aspirate the BAL, then do the same with subsequent syringes until a minimum volume of 10 ml is obtained.

5. Combine the collected BAL fluid from each syringe into a sterile container and label this as a BAL for the PHARLAP study.

6. If the patient has been assigned to the PHARLAP group, this procedure should now be followed as soon as possible by a combined open lung procedure (see page 26) if it is day 1 or a BRM if it is day 3.

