There is substantial experimental evidence, biological rationale, and supportive clinical evidence to suggest the efficacy of the PHARLAP ventilation strategy in ARDS. However, mostly because of concern that SRM's and high PEEP may cause barotrauma and haemodynamic instability in critically ill patients, previous trials may have been sub-optimally designed to determine the true efficacy of such an OLS. The PHARLAP strategy is more intensive, more individual patient tailored and at least as safe as previously studied open lung strategies. In addition, the PHARLAP strategy can be delivered by almost any clinician using any conventional mechanical ventilator and if proven effective and safe, would be highly applicable for widespread use (including the developing world). Given the significance and cost of ARDS, the possible benefits of this strategy, the growing number of recommendations for the use of a LRM with elevated levels of PEEP^{18,19,46}, this study is an important undertaking. The trial will determine whether the PHARLAP ventilation strategy is effective in increasing ventilator free days in patients with ARDS. If the PHARLAP strategy is proven to improve ventilator free days it will provide a strong impetus to conduct an international phase III RCT to determine the effects of this strategy on mortality.

OBJECTIVES

Aim

To determine the efficacy of the PHARLAP strategy compared to a control ventilation strategy in increasing ventilator free days assessed during the 28 days post randomisation.

Hypothesis

The PHARLAP strategy group will have a higher number of ventilator free days at day 28 than the control group.

STUDY OUTCOME MEASURES

Primary outcome

- Number of ventilator free days at day 28 post randomisation

Secondary outcome

- Physiological outcomes:
 - PaO₂/FiO₂ ratio
 - Static lung compliance
- Inflammatory outcomes:
 - Baseline to day 3 change in IL-8 and IL-6 concentrations in broncho-alveolar lavage fluid
 - Baseline to day 3 change in IL-8 and IL-6 concentrations in plasma
- Clinical/patient-centred efficacy outcomes:
 - Use of rescue therapies for severe hypoxaemia – inhaled nitric oxide, inhaled prostacyclin, prone positioning, high frequency oscillatory ventilation and extracorporeal membrane oxygenation (ECMO)
 - Incidence of acute kidney injury (AKI)
 - ICU and hospital length of stay
 - Quality of life assessment (SF-36v2 and EQ-5D) at 6 months
 - Mortality at ICU/hospital discharge, 28 days, 90 days and 6 months

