- The expiratory pause should be removed, and 30 seconds waited, before a 0.5 second inspiratory pause should be set to measure plateau pressure.
- Within the same breath, expired tidal volume and plateau pressure should be measured.
- Static respiratory compliance should be calculated as tidal volume / (plateau pressure – total PEEP).

Collection of specimens at baseline:

Patients in both groups should have specimens of blood and bronchoalveolar lavage (BAL) fluid collected prior to commencement of the assigned mechanical ventilation strategy.

The blood specimen should be collected from the arterial line and sent with the BAL specimen to the site's pathology department for appropriate spinning and storage. These will be sent in batches to Flinders Medical Centre for measurement of IL-6 and IL-8 levels in both blood and BAL.

To perform the BAL, we recommend using a bronchoscopic method. Alternatively a non-bronchoscopic technique using the KimVent BAL Cath (Bronchial Aspirate Sampling Catheter) can also be used. There are two sizes of KimVent BAL Caths – 13F is recommended for a size 7cm ETT and smaller and 16F is recommended for a size 7.5cm ETT and larger. These will be provided to all sites by the ANZIC-RC. Whichever method is used, at least 10 ml of BAL fluid should be collected. A right-sided BAL is preferred for consistent sampling.

Appendix 2 includes instructions on how to collect the specimen if a bronchoscopic method is used. It also includes instructions on how to perform the non-bronchoscopic technique using the KimVent BAL Cath to collect the BAL specimen.

If the patient has been assigned to the PHARLAP group, this procedure should now be followed as soon as possible (but no later than 4 hours after randomisation) by a combined open lung procedure (see below). Satisfactory haemodynamic resuscitation may also be required before 4 hours after randomisation.

If it is not feasible to collect a BAL sample because of limited resources to perform the bronchoscopy or the Investigator is unfamiliar with the use of the KimVent BAL cath or it may cause undue delay in recruitment then

a BAL sample is not required to be collected once enrolled. We understand that this may occur from time to time. However, every attempt should be made to collect the blood sample on all patients.

Control group mechanical ventilation

Initial commencement of mechanical ventilation in the control group

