Titration of the FiO₂ and PEEP: The FiO₂ and PEEP should be set using the table of allowable FiO₂ and PEEP combinations as a guide. The PEEP level in this table represents the PEEP level set on the ventilator, not total PEEP. The settings should be as far to the left of this chart as possible, thereby using the lowest combination of FiO₂ and PEEP possible while maintaining oxygenation within the target range.

If the SaO₂ is < 90% (or PaO₂ < 60 mmHg, if available), the patient should be changed to the FiO₂ and PEEP combination to the right of the current settings. If the patient has a significant desaturation, it is permissible to rapidly increase the PEEP/FiO₂ from left to the right of the chart as quickly as required to achieve a satisfactory oxygen saturation, then titrate the PEEP/FiO₂ to achieve a SaO₂ 90 – 95%.

FiO ₂	0.3	0.4	0.4	0.5	0.5	0.6	0.7	0.7	0.7	0.8	0.9	0.9	0.9	1.0
PEEP (cmH ₂ O)	5	5	8	8	10	10	10	12	14	14	14	16	18	18-24

If the SaO₂ is > 95% (or PaO₂ > 80 mmHg, if available), the patient should be changed to the FiO₂ and PEEP combination to the left of the current settings. If this leads to a reduction in PEEP, it is preferable not to reduce the PEEP again **before 4 hours have passed.**

Ventilation during patient transfers: Mechanical ventilation should continue to adhere to this control group strategy during patient transfers (to diagnostic or therapeutic procedures outside the ICU) where possible. However if the patient receives mechanical ventilation using either a manual (hand-bagging) circuit or a transport ventilator that is not practically able to deliver the control group mechanical ventilation settings, patients may be ventilated using alternative means whilst away from the ICU. Resumption of control group mechanical ventilation should occur as soon as possible after the transfer.

Specific measurements on Day 3 in the control group

Patients in both groups should have 2 things measured on day 3:

1. Static respiratory compliance should be measured (see page 22 for technique).
2. Specimens of blood and BAL should be collected (see below) – **after** static respiratory compliance has been measured. The BAL should be collected using the same technique as was used at baseline.

Transition from controlled to spontaneous mechanical ventilation in the control group

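### The lavage recipe fixes recovered volume but not instilled volume, so dilution can add noise to the IL-6 and IL-8 concentration-change outcome

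*Combined protocol and SAP*

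**What the plan says.** Both methods in Appendix 2 start from the same preparation: "Draw up 60 ml of 0.9% saline in appropriate syringes (usually three 20 ml syringes"). The non-bronchoscopic method injects and aspirates the first syringe, "then do the same with subsequent syringes via the 3 way port until a minimum volume of 10ml. is obtained". The bronchoscopic method has the same rule: "then do the same with subsequent syringes until a minimum volume of 10 ml is obtained". In both, the returns become one specimen: "Combine the collected BAL fluid from each syringe into a sterile container and label this as a BAL for the PHARLAP study". The non-bronchoscopic method alone has an additional step before wedging: "Flush the catheter with 5 ml 0.9% saline".

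The main text (Collection of specimens at baseline) sets only a floor on recovery: "Whichever method is used, at least 10 ml of BAL fluid should be collected". For day 3, the Specific measurements sections for both groups say: "The BAL should be collected using the same technique as was used at baseline". That fixes the method but not the volume.

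The outcome, under Study outcome measures, is "Baseline to day 3 change in IL-8 and IL-6 concentrations in broncho-alveolar lavage fluid". Appendix 7 uses the lavage change alongside the plasma change. The Laboratory sampling section says that protein is assayed as well as the two cytokines, but neither the outcome definition nor the Statistical and analytical plan says what protein is for.

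**The concern.** A cytokine concentration in lavage fluid depends on how much saline the lining fluid was mixed with. Here the amount of saline is set by how readily fluid comes back, and so is not constant. A patient who needs one syringe at baseline and three on day 3 would show a fall in concentration with no biological change, and the reverse pattern would show a rise.

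At stake is the precision of the lavage IL-6 and IL-8 comparison, which is a stated secondary outcome and one of the two inflammatory measures in Appendix 7. Lavage may be skipped where it is not feasible, so fewer than 340 pairs may exist and lost precision matters more. The primary outcome and the plasma cytokines are not affected.

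**Working it through.** **Inputs from the documents.** Saline drawn up: 3 × 20 = 60 ml, which reproduces the stated total. Recovery needed: at least 10 ml.

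**Permitted range.** Instilled volume at stopping is 20, 40 or 60 ml (25, 45 or 65 ml if the 5 ml catheter flush is counted). Stopping after one, two or three syringes needs a cumulative return of 10/20 = 50%, 10/40 = 25% or 10/60 = 16.7%.

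**Assumptions, because the documents give no figures.**
- Lining-fluid volume V is 0.5 to 5 ml, with full mixing.
- One, two or three syringes are equally likely, and independent on the two days.
- The biological SD of the log change, S, is 0.8, 1.0 or 1.5.

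**Formulas.** Let d be the dilution relative to one syringe. Added variance of the log change: v = 2 × Var(ln d). Loss of effective sample size: v / (S² + v).

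**Upper bound: concentration strictly inverse to total saline.** Here d = 1, 2, 3. Var(ln 1, ln 2, ln 3) = 0.206, so v = 0.41. The loss is 0.41/(0.64 + 0.41) = 39%, 0.41/(1.00 + 0.41) = 29% and 0.41/(2.25 + 0.41) = 15%.

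**The recipe as written: aspirate each syringe in turn, then pool.** Early, less diluted returns stay in the specimen. Worked example with V = 1 ml and lining-fluid concentration 1:
- One syringe: 1/21 = 0.0476.
- Two syringes returning 5 ml each: the first return is at 0.0476. The remaining 16 ml hold 16/21 = 0.762 units. After another 20 ml the concentration is 0.762/36 = 0.0212. The pooled value is (0.0476 + 0.0212)/2 = 0.0344, so d = 0.0476/0.0344 = 1.38.
- Three syringes by the same steps: d = 1.70.

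Results over V = 0.5 to 5 ml:

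| Model | d, two syringes | d, three syringes | v | Loss, S = 0.8 | S = 1.0 | S = 1.5 |
|---|---|---|---|---|---|---|
| Equal returns totalling 10 ml | 1.33–1.39 | 1.61–1.71 | 0.08–0.10 | 11–13% | 7–9% | 3–4% |
| Later returns larger (4+8 ml; 2+4+8 ml) | 1.48–1.58 | 2.01–2.20 | 0.16–0.21 | 20–25% | 14–17% | 7–9% |
| Strict proportionality (upper bound) | 2 | 3 | 0.41 | 39% | 29% | 15% |

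**Sensitivity to the split.** Suppose 80/15/5% of patients need one, two or three syringes, and take the largest sequential dilutions (1.58 and 2.20; logs 0.455 and 0.790). The mean log is 0.15 × 0.455 + 0.05 × 0.790 = 0.108. The variance is 0.15 × 0.207 + 0.05 × 0.624 − 0.108² = 0.051, so v = 0.10. The loss at S = 0.8 is 0.10/0.74 = 14%.

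**Bias, illustration only.** Suppose 40/40/20% of controls and 60/30/10% of PHARLAP patients needed one, two or three syringes on day 3. With no true difference, the PHARLAP to control ratio would be exp[(0.4 − 0.3) ln d₂ + (0.2 − 0.1) ln d₃] = (d₂ × d₃)^0.1. That is 1.08–1.09 with equal returns, 1.12–1.13 with later-weighted returns, and 6^0.1 = 1.20 under strict proportionality.

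**The case against.** Several points on the other side stand.

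- **Size.** The range of 20 to 60 ml is what the recipe permits, not what was observed. The protocol gives no return data, and one syringe suffices whenever half the fluid returns. A reader might infer a threefold dilution. The recipe does not support that as a working figure, because returns are removed in turn and pooled.
- **Independence.** The same patient, the same technique and a preferred right-sided sample make some correlation between days plausible, which would shrink the noise.
- **Bias between arms.** A reader might infer that the PHARLAP comparison is biased. Lavage leaves PEEP as set, the PHARLAP minimum is 15 cmH₂O until weaning, and the control chart starts at 5, so conditions at the day-3 lavage can differ by arm. But nothing in the documents shows that PEEP or recruitment changes fluid return, and the splits in the illustration are invented.
- **Recording.** A reader might infer that volumes go unrecorded. The Data variables collected list contains neither volume, but it consists of broad headings and does not name the cytokines either. The case report form is not in the documents.
- **Importance.** A reader might take lavage as the main outcome of the substudy. Appendix 7 lists lavage and plasma cytokines side by side.
- **Later correction.** The full analysis plan was still to be finalised and protein is assayed, so a correction could be added. That does not help with volumes if they were not noted at the bedside.

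What remains is that the written stopping rule lets dilution enter a concentration outcome, and no stated step takes it out.

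**Conclusion.** The concern holds as a moderate weakness in one secondary outcome. Instilled saline can range from 20 to 60 ml between patients and between visits, and the outcome is the change in raw concentration with no stated correction. The main effect is noise: a loss of roughly 3% to 25% of effective sample size for S from 1.5 down to 0.8, with 15% to 39% as the upper bound. These figures rest on assumed lining-fluid volumes, equal thirds and independent days. A split dominated by one syringe, or correlation between days, would reduce them. Bias between arms is possible and its size unknown. The documents do not establish it.

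**What to change.** 1. In both Appendix 2 methods, record the number of syringes and the volumes instilled and recovered, at baseline and on day 3.
2. On day 3, aim for the same number of syringes as that patient's baseline lavage, within the 60 ml already drawn up and where feasible. Keep the 10 ml minimum recovery, and record any departure. Strict matching is not proposed, because it could conflict with that minimum.
3. In the analysis plan, make log day-3 concentration adjusted for log baseline concentration the main lavage comparison.
4. Prespecify two sensitivity analyses, one adjusted for instilled volume and one corrected for protein. State that day-3 volume and protein may themselves respond to treatment, which is why neither belongs in the main comparison.

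Matching syringe number does not equalise recovery, so some variation in dilution will remain. The cost is a few case report form fields, a little more analysis work, and sometimes an extra syringe on day 3. No new assay is needed.

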APPENDIX 3: SCHEDULE OF EVENTS

Assessments/ Procedures	Pre Randomisation/ Baseline	Day 1	Day 2	Day 3	Day 4	Day 5	Day 6 till liberation of mechanical ventilation	ICU discharge	Hospital discharge	Follow-up 28 days	Follow-up 90 days	Follow-up 6 months
Inclusion & Exclusion criteria	X											
Consent	X											
Randomisation	X											
Demographic data	X											
Height & weight measurement	X											
CXR	X											
Download CXR image	X											
Apache II score	X											
Apache III diagnosis	X											
SOFA score	X	X	X	X	X	X	X					
Ventilation observations	X	X	X	X	X	X	X					
Static respiratory compliance		X		X								
Combined open lung procedure		X*	X*	X*	X*	X*						

* Only for patients randomised to PHARLAP treatment group (combined open lung procedure)

Assessments/ Procedures	Pre Randomisation/ Baseline	Day 1	Day 2	Day 3	Day 4	Day 5	Day 6 till liberation of mechanical ventilation	ICU discharge	Hospital discharge	Follow-up 28 days	Follow-up 90 days	Follow-up 6 months
Sputum sample (BAL)		X		X								
Blood sample		X		X								
Adverse events		X	X	X	X	X	X	X				
Serious adverse events		X	X	X	X	X	X	X	X			
Survival status								X	X	X	X	
SF36V ₂												X
EQ5D												X

APPENDIX 4: APACHE II SEVERITY OF DISEASE CLASSIFICATION

APACHE II CALCULATION WORKSHEET

The APACHE II score is derived from 3 scoring systems: **Part A** – Acute Physiology Score, **Part B** – Age Points, **Part C** – Chronic Health Points

Part A - Acute Physiology Score

For each of the 12 physiological variables, select the value **closest in time**, but prior, to the patient meeting the final entry criteria for inclusion into the study (**T0** hours). Enter the value in the right hand column.

For exact non-integer data that is not found in any of the given ranges, round the figure up or down to the nearest whole number. Eg, 44 years and 3 months is rounded down to ≤ 44 years and assigned 0 points; a calculated MAP of 129.7 is rounded up to 130 and assigned 3 points. For integers of xx.5 always round upwards. This is an arbitrary decision but must be followed for every patient to ensure consistency.

1. **Temperature** – this should be a core temperature measurement (rectal, tympanic, oesophageal or via PAC). Where this is not possible, add 0.5°C to the oral or axillary temperature
2. If mean arterial pressure (**MAP**) is not calculated by monitoring equipment, use the manual sphygmomanometer recording of systolic (SBP) and diastolic blood pressure (DBP) to obtain MAP using this equation $\text{MAP} = (\text{DBP} \times 2) + \text{SBP} \div 3$.
3. If the patient has an atrial arrhythmia, measure the ventricular response rate (R waves) only to record the **heart rate**.
4. **A – aDO₂** is the difference between the calculated alveolar oxygen tension and the arterial oxygen tension. The alveolar oxygen tension is calculated by this equation: $\text{AO}_2 = 713 \times \text{FiO}_2 - \text{PaCO}_2 \times 1.25$. The FiO_2 here is expressed as a proportion of a unit. e.g. 100% $\text{FiO}_2 = 1$ and 60% equals 0.6. If the FiO_2 (inhaled oxygen concentration) is greater than 50%, record the most deranged value for the **A – aDO₂**. If the FiO_2 is less than 50% record only the **PaO₂** (arterial oxygen pressure). All measurements are in mmHg.
5. If ABGs have not been performed, choose the most deranged value for the serum venous bicarbonate (HCO_3) in place of the **arterial pH**
6. To obtain a score for the Glasgow Coma Scale (**GCS**) use the GCS worksheet provided and subtract the GCS score from 15 to arrive at a score on the APACHE worksheet.

Whenever possible, make an attempt to obtain a score for each physiological variable. If one of the 12 variables is not available, assign 0 points and make a note of this absence on the APACHE II worksheet. The assumption being made is that a test or measurement was not ordered because the status of the patient did not warrant investigation, rather than the data was missing.

To complete **Part B** – assign points to the age range that the patient fits in to. eg, a 48 year old patient would be assigned 2 points.

To complete **Part C** – first decide if the patient meets any of the criteria provided on the worksheet for a history of severe organ insufficiency or immunocompromised. If there is no history, assign 0 points. If there is a history, assign points depending on whether the patient is an non-operative emergency admission or an emergency post-operative admission

Finally, add the points recorded for each of the 3 parts and enter this total score at question 1.7 The minimum score is 0 and the maximum score is 71. Keep the completed APACHE II worksheet in the documentation folder for this patient. It may be used for quality assurance measures. You will therefore need to print your hospital ID, Patient Initials and Patient Study Number on the APACHE worksheet

BASELINE DATA

APACHE II Severity Of Disease Classification

Patient Study Number

--	--	--	--	--	--

A. ACUTE PHYSIOLOGY SCORE (APS)	PHYSIOLOGIC VARIABLE	High Abnormal Range				0	Low Abnormal Range				APS Scores
		+4	+3	+2	+1		+1	+2	+3	+4	
	Temperature – rectal (°C)	≥ 41	39 – 40.9		38.5 – 38.9	36 – 38.4	34 - 35.9	32 – 33.9	30 – 31.9	≤ 29.9	
	Mean arterial pressure – mmHg	≥ 160	130 - 159	110 – 129		70 - 109		50 - 69		≤ 49	
	Heart rate (ventricular response)	≥ 180	140 – 179	110 – 139		70 - 109		55 - 69	40 - 54	≤ 39	
	Respiratory rate (non-ventilated or ventilated)	≥ 50	35 – 49		25 - 34	12 - 24	10 - 11	6 - 9		≤ 5	
	Oxygenation: A - aDO ₂ or PaO ₂ (mmHg)	> 500	350 – 499	200 – 349		< 200					
	a. if FIO ₂ ≥ 0.5 record A - aDO ₂					PO ₂ -> 70	PO ₂ 61 - 71		PO ₂ 55- 60	PO ₂ < 55	
	b. if FIO ₂ < 0.5 record only PaO ₂										
	Arterial pH	≥ 7.7	7.6 – 7.69		7.5 – 7.59	7.33 – 7.49		7.25 – 7.32	7.15 – 7.24	< 7.15	
	Serum sodium (mMol/L)	≥ 180	160 – 179	155 – 159	150 - 154	130 - 149		120 - 129	111 - 119	≤ 110	
	Serum potassium (mMol/L)	≥ 7	6 – 6.9		5.5 – 5.9	3.5 – 5.4	3 – 3.4	2.5 – 2.9		≤ 2.5	
	Serum creatinine (mMol/L) (double point score for acute renal failure)	≥ 0.300	0.171-0.299	0.121-0.17		0.05-0.12		< 0.05			
	Haematocrit (%)	≥ 60		50 – 59.9	46 – 49.9	30 – 45.9		20 – 29.9		< 20	
	White blood count (total/mm ³) (in 1,000s)	≥ 40		20 – 39.9	15 – 19.9	3 – 14.9		1 – 2.9		< 1	
	Glasgow Coma Score (GCS) (Score = 15 minus actual GCS)										
	Serum HCO ₃ (venous – mMol/L) (Only use this if no ABGs available)	≥ 52	41 – 51.9		32 – 40.9	22 – 31.9		18 – 21.9	15 – 17.9	< 15	

B. AGE POINTS			C. CHRONIC HEALTH POINTS			
Assign points to age as follows:	Age (yrs)	Points	If patient has history of severe organ system insufficiency or is immuno-compromised, assign points as follows:	Points	DEFINITIONS: Organ insufficiency or immuno-compromised state must have been evident prior to this hospital admission and conform to the following criteria:	
	 ≤ 44	0			LIVER	Biopsy proven cirrhosis & documented portal hypertension (PH); episodes of upper GI bleeding due to PH; or prior episodes of hepatic failure/encephalopathy/coma
	 45-54	2	 a. for non-operative or emergency post-operative patients	5	RENAL	Receiving chronic dialysis
	 55-64	3			CARDIOVASCULAR	New York Heart Association Class IV
	 65-74	5	 b. for elective post-operative patients	2	RESPIRATORY	Chronic restrictive, obstructive or vascular disease resulting in severe exercise restriction (i.e. unable to climb stairs, perform household duties); or documented chronic hypoxia hypercapnia, 2 ^o polycythemia, severe pulmonary hypertension (>40mmHg) or respiratory dependency
 ≥ 75	6	IMMUNOCOMPROMISED			Patient has received therapy that suppresses resistance to infection, eg. immuno-suppression, chemotherapy, radiotherapy, long term or recent high dose steroids, or has a disease sufficiently advanced to suppress resistance to infection (eg leukaemia, lymphoma, AIDS)	

APACHE II SCORE - a sum of:	A. APS points = ____	B. Age points = ____	C. Chronic Health points = ____	Sum of A + B + C = _____ (0 to 71)
------------------------------------	----------------------	----------------------	---------------------------------	---

For intubated patients use verbal scoring column allocated

Best Verbal Response

5	Orientated
4	Confused
3	Inappropriate
2	Incomprehensible
1	No Response

"Verbal" Intubated

[figure not shown]
5	Orientated
3	In Between
1	No Response

Best Motor Response

6	Obeys
5	Localises
4	Flexion – Withd.
3	Flexion – Decort.
2	Extension
1	No Response

Best Eye Opening

4	Spontaneous
3	To Command
2	To Pain
1	No Response

